3 STUDY OBJECTIVES AND ENDPOINTS

3.1 Primary Objective

The primary objective of this study is to assess the long-term safety and tolerability of 10, 10, 20 mg/kg ataluren in subjects with nmDBMD who had prior exposure to ataluren in a PTC-sponsored clinical trial.

3.2 Secondary Objectives

Secondary objectives include the following:

- Ambulatory subjects (able to run/walk 10 meters in ≤ 30 seconds) - To determine the effect of ataluren on ambulation and other aspects of physical function
- Nonambulatory subjects (unable to run/walk 10 meters in ≤ 30 seconds) - To assess the effect of ataluren on activities of daily living, upper limb function, and pulmonary function
- All subjects - To assess subject and/or parent/caregiver reports of changes in disease status:
 - i. Retrospectively during and after participation in previous studies (Studies 007 and 007e)
 - ii. Prospectively during the current study

3.3 Study Endpoints

Primary:

- Safety profile characterized by type, frequency, severity, timing, and relationship to ataluren of any adverse events or laboratory abnormalities

Secondary:

- In ambulatory subjects,
 - i. change from baseline in 6MWD as measured by the 6-minute walk test (6MWT)
 - ii. change from baseline in physical function as measured by the North Star Ambulatory Assessment (NSAA)
 - iii. change from baseline in timed function tests (time to stand from supine and time to run/walk 10 meters)
- In non-ambulatory subjects,
 - i. change from baseline in pulmonary function test - % predicated forced vital capacity (FVC) and % predicted forced expiratory volume in 1 second (FEV1) as measured by spirometry
 - ii. change from baseline in patient and parent/caregiver-reported activities of daily living, as measured by the Egen Klassifikation (EK) scale

- All subjects,
 - i. changes in patient and/or parent/caregiver reports of disease status as measured by a standardized survey administered by site personnel

3.4 Sample Size

The sample size, up to ~96 subjects, was determined by how many subjects satisfy all inclusion/exclusion criteria when applying for participation in this study and not by any formal statistical hypothesis.

5 STATISTICAL ANALYSIS

5.1 General Statistical Considerations

Summary tables for continuous variables will contain the following statistics: n, mean, standard deviation, standard error, 95% confidence intervals (CIs) on the mean, median, minimum, and maximum. Summary tables for categorical variables will include N, n, and percentages. In by-visit summaries, the analysis visits will be derived via visit mapping windows.

By-patient listings will be created for each CRF module. The data will be listed by center/subject ID and visit.

In addition, all analyses will be performed by corticosteroid use (yes or no before or during the study), by ambulatory status (ambulatory or non-ambulatory) at baseline, and overall, unless specified otherwise.

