5.8 Secondary Variables

Subject [REDACTED] will be excluded from the As-Treated population in the analyses of all secondary endpoints.

5.8.1 6-Minute Walk Test

The distance walked at each visit and the change from baseline at each post baseline visit, as obtained from the 6-minute walk test (6MWT), will be summarized descriptively for ambulatory subjects with non-missing baseline 6MWT assessments. The distance walked at each will also be summarized for each actual age.

The endpoint will also be analyzed by means of a mixed model repeated measures (MMRM). An unstructured variance-covariance will be assumed and the estimation method will be the default, ReML. The model will include the factors for treatment, visit, age (6-11, 12-17, and ≥ 18 years), use of corticosteroids at baseline (yes vs no), and baseline 6MWD category (< 300 meters, ≥ 300 - < 400 meters, ≥ 400 meters), and baseline 6MWD as a covariate. Visit is considered as a categorical variable. From this analysis the mean change at each visit will be evaluated. If the model cannot converge, compound symmetry variance-covariance structure will be assumed.

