5.8.2 Timed Function Tests

Timed function test data (ie, time to stand from supine and time to run/walk 10 meters) and change from baseline to each post baseline visit will be summarized descriptively by visit for ambulatory subjects with non-missing baseline timed function tests assessments. Similarly the time to stand from supine and time to run/walk 10 meters will also be summarized for each actual age.

Timed function test (TFT) data imputation rules as the following will be used in the summary.

- If time to run/walk 10 meters > 30 sec, then set to 30 sec.
- If time to stand from supine > 30 sec, then set to 30 sec.

Similar to 6MWT, the time to stand from supine and time to run/walk 10 meters of will also be analyzed by means of a mixed model repeated measures (MMRM) where baseline is baseline time taken to stand from supine and time taken to run/walk 10 meters, respectively.

The Kaplan-Meier method will be applied to the analysis of age at loss of ambulation. The median age at loss of ambulation will be reported by corticosteroids use at baseline. The Kaplan-Meier curves will also be displayed. The age at loss of ambulation is defined as age of the disease progression reported as the adverse event or age at the time to run/walk 10 meters > 30 seconds, whichever occurs earlier. The subjects who are ambulatory at the end of study or discontinuation will be censored on the last valid timed function tests assessment date. Age on that date will be used in the analysis. A sensitivity analysis will be performing based on the loss of ambulation defined only by disease progression AE.

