5.8.5 Spirometry

Pulmonary function parameters of %-predicated FVC, %-predicted FEV1 (adjusted using ulna length and age), peak expiratory flow (PEF), and peak cough flow (PCF) and their absolute and relative changes from baseline will be summarized by visit for non- ambulatory subjects and As-Treated population. Similarly the observed values of the endpoints will also be summarized for each actual age.

The Kaplan-Meier method will be applied to the analysis of age at FVC <1 liter. The median age at FVC<1 liter will be reported by corticosteroids use at baseline. The Kaplan-Meier curves will also be displayed. The age at FVC<1 liter is the one at the first time FVC<1 liter. If subjects do not have FVC<1 liter, the age at the last non-missing FVC assessment will be chosen as the censor age.

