5.9.2 Corticosteroids type subgroups

The by-visit summary on the observed values and change from baseline to each post baseline visit values will be performed descriptively for each corticosteroid type prior to study entry (deflazacort vs prednisone/prednisolone) on 6MWT and TFTs. The Kaplan-Meier method will be applied to the analysis of age at loss of ambulation and age at FVC <1 liter each subgroup.

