5.9.3 Cumulative duration of corticosteroids use subgroups

The cumulative duration of corticosteroid use prior to study entry will be categorized as <12 months vs ≥12 months. The by-visit summary on the observed values and change from baseline to each post baseline visit values will be performed descriptively for each subgroup on 6MWT and TFTs. The Kaplan-Meier method will be applied to the analysis of age at loss of ambulation and age at FVC <1 liter for each subgroup.

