Demographics and baseline characteristics (age, race, ambulation status, corticosteroid use (yes or no), duration of corticosteroid use, corticosteroid type, baseline 6MWD, baseline time to run/walk 10 meters, baseline time to stand from supine, baseline %-predicted FEV1, %-predicted FVC, PEF, EK score, NSAA total score) will be summarized descriptively for CINRG and Study 019 based on each matched population. The summary will be displayed by corticosteroid use (yes vs no) and cumulative steroid use (≥ 12 months vs < 12 months) for baseline ambulatory and non-ambulatory subjects separately. In general, the baseline is defined as the first visit in CINRG data. The baseline age in the FVC analysis using piece-wise regression models is the age at the first FVC assessments for both CINRG and Study 019.

The comparison to the natural history data (ie, CINRG data) based on matched subjects will be performed in FVC using piece-wise regression models, age to loss of ambulation, and age to FVC < 1 liter using Kaplan-Meier method.

Piece-wise regression models will be applied to log FVC in CINRG and Study 019 data, separately, using different ages as the changepoint. The most possible changepoint in terms of age will be chosen at the best model fit (ie, AICC value is the maximal). Scatter plots of log FVC and the most fitted piece-wise regression line will be generated for CINRG and Study 019, separately. Comparison between the observed and predicted FVC in Study 019 will be performed using repeated measures analysis of variance to account for within-subject correlation, where the predicted values are based on the regression equation estimated by the best fit regression model based on CINRG data.

The Kaplan-Meier method will be applied to the analysis of age to loss of ambulation and age to FVC < 1 liter. The median age to loss of ambulation and median age to FVC < 1 liter will be reported. The comparison between Study 019 and CINRG will be conducted via log-rank test by corticosteroid use at baseline (yes or no) and overall. The Kaplan-Meier curves will also be displayed.

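### The default corticosteroid split in SAP 5.1 uses on-study steroid use, unlike the baseline split used elsewhere in the SAP, and can distort the by-steroid safety and descriptive tables in either direction

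*SAP*

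**What the plan says.** SAP 5.1 sets a default: "all analyses will be performed by corticosteroid use (yes or no before or during the study"). The same sentence continues "by ambulatory status (ambulatory or non-ambulatory) at baseline, and overall, unless specified otherwise". Ambulatory status is thus fixed at entry, while steroid status can be settled by anything up to the end of follow-up.

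Later sections replace the default for particular analyses:

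- SAP 5.8.1, 6MWD MMRM (and by reference the timed function MMRMs in 5.8.2): "use of corticosteroids at baseline (yes vs no").
- SAP 5.8.2: "The median age at loss of ambulation will be reported by corticosteroids use at baseline".
- SAP 5.8.5: "The median age at FVC<1 liter will be reported by corticosteroids use at baseline".
- SAP 8.2.1, comparison with the natural-history data: "via log-rank test by corticosteroid use at baseline (yes or no) and overall". The by-age natural-history summaries also use baseline status.
- SAP 5.9.2: "for each corticosteroid type prior to study entry (deflazacort vs prednisone/prednisolone) on 6MWT and TFTs".
- SAP 5.9.3: "The cumulative duration of corticosteroid use prior to study entry will be categorized as <12 months vs ≥12 months".

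By-visit vital signs, ECG and LVEF are summarised for all subjects together. Exposure and compliance are shown overall and by ambulatory status.

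SAP 5.5 plans to count boys who switch on to or off steroids. Protocol 10.3 asks for summaries by corticosteroid use but gives no timing.

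**The concern.** A subgroup defined by on-study use sorts boys by something that happens after treatment starts. Three things follow. A later starter's results from before his first steroid dose are reported as a user's results. His pre-steroid time enters the user denominator of the exposure-adjusted adverse event rates in SAP 5.7.1. And a boy followed for longer has more chance to become a user, so the groups differ in follow-up by construction.

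The affected tables include the primary endpoint, which is safety. The protocol gives reasons to look at safety by steroid use. Section 6.4.5 says that hypertension may be more frequent with ataluren plus steroids than with steroids alone. Section 13.2.3.5 reports that all six boys with hypertension events in Study 007 were on steroids. Section 13.2.3.2.2 says that ACTH and cortisol are generally low, and adrenal monitoring less sensitive, in boys taking steroids.

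There is also a reporting problem. The same boy can be a user in the descriptive 6MWT table and a non-user in the MMRM for the same endpoint.

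**Working it through.** The plan states no power, error rate or event figure for the steroid subgroups, so there is no planned figure to reproduce. The check has two parts: which tables the default reaches, and what it can do there.

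**Reach of the default**

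| Output | Steroid status used |
|---|---|
| MMRM for 6MWD and timed function tests | baseline |
| Kaplan-Meier age at loss of ambulation and at FVC <1 liter | baseline |
| Natural-history log-rank tests and by-age summaries | baseline |
| Steroid type and duration subgroups | before study entry |
| By-visit vital signs, ECG, LVEF, exposure | no steroid split |
| Adverse event and laboratory tables | default (before or during) |
| By-visit 6MWT, timed function, NSAA, EK, spirometry summaries | default |
| Disposition, baseline characteristics, disease status survey | yes/no without timing, so apparently default |

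**Illustration 1: steroids have no effect on anything**

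From the documents: up to about 96 boys and 240 weeks. Assumed: 60-90% users at entry, 20-50% of the rest starting over 240 weeks, 30% dropout, and constant rates independent of each other.

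One case in full, with 75% users at entry (24 non-users) and a 50% start probability:

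- Cumulative hazards over 240 weeks: dropout D = -ln(0.70) = 0.357; start S = -ln(0.50) = 0.693.
- Share of entry non-users never seen to start = e^-(S+D) + [D/(S+D)] x [1 - e^-(S+D)] = 0.35 + 0.340 x 0.65 = 0.571.
- Size of the non-user group = 24 x 0.571 = 13.7 boys.
- Completion among non-users = 0.35/0.571 = 61%.
- Completion among users = (0.70 - 0.25 x 0.35)/(1 - 0.25 x 0.571) = 0.6125/0.857 = 71%.

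With a 20% start probability the share is 0.56 + 0.615 x 0.44 = 0.831. That leaves 19.9 boys in the non-user group, with completion of 0.56/0.831 = 67%.

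Simulation over the full assumed ranges gave:

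| | Default: users | Default: non-users | First-dose split: both groups |
|---|---|---|---|
| Completion | 70-73% | 61-67% | 70% |
| Mean follow-up (weeks) | 202-207 | 185-197 | about 202 |
| Boys with at least one event (true 240-week risk 30%) | 25.5-26.1% | 23.6-25.2% | about 25.5% |

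The gaps come only from the grouping. With constant rates and no steroid effect, the exposure-adjusted rate itself would not shift; the crude percentages do.

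**Illustration 2: starting depends on the outcome**

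Assume that half of all boys decline whatever their steroid use, and that 60% are users at entry. Of the 40% who are not, 20% decline and 20% do not.

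- Decliners start with probability 40%, the others with 10%. Non-users: 0.12/(0.12 + 0.18) = 40% decline. Users: (0.30 + 0.08)/0.70 = 54%.
- Probabilities reversed. Non-users: 60%. Users: (0.30 + 0.02)/0.70 = 46%.
- Equal probabilities and equal follow-up: 50% in both groups.

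With 60-90% users at entry, the user figure is 51-54% in the first case and 46-49% in the second. The direction depends on why boys start.

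**Person-time**

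SAP 5.7.1 counts 48 weeks as a year, so 240 weeks are 5 patient-years. A boy who starts steroids at week 120 puts 2.5 of his 5 years into the user denominator before any exposure. If the event rate is r off steroids and kr on them, he contributes r(1+k)/2 to the user group instead of kr. A first-dose split makes the reverse error: his 2.5 years on steroids are counted as non-user time.

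**The case against.** The strongest reply is that the default reaches less than its opening words suggest. The sentence allows exceptions, and every modelled, time-to-event or natural-history analysis that names a steroid variable uses baseline or pre-entry status. This stands. A reader might infer that all by-steroid results are affected, or that 5.8 contradicts 5.1. Neither follows, because the later sections are overrides that 5.1 permits.

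Secondly, bias is possible but not shown. No count of on-study starters is given. If no boy first starts on study, none is classified by future use. The affected tables are descriptive, in a single-arm study without a formal hypothesis, and SAP 5.5 will show how many boys switch. This also stands, and it limits the point to what the split can do.

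Thirdly, a reader might picture the non-user group as boys who never needed steroids and predict a direction from that. Protocol 1.1 points elsewhere: steroids are sometimes withheld because of serious side effects, especially in nonambulatory patients. The documents support no direction.

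Fourthly, an ever-used split keeps the non-user group free of steroid exposure, which a first-dose split does not. This is right for adverse events and shapes the fix. Counting a past user as a user rests on information from before entry, so it is a choice of definition and not conditioning on the future.

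What remains is that the default governs the primary safety tables, gives no reason for treating steroid status differently from ambulatory status, and leaves two user groups with different members in one report.

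**Conclusion.** The concern holds for the default split only. It uses post-baseline information and differs from the baseline definition in SAP 5.8.1, 5.8.2, 5.8.5 and 8.2.1. Where it applies, it can bias the user versus non-user contrast in either direction.

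The size cannot be stated from the documents. Under the assumed ranges with no steroid effect, the spurious gap is modest for the share of boys with an event and larger for completion and follow-up. If starting is linked to outcome, the distortion falls mainly on the smaller non-user group: 40% or 60% decline against a true 50%. These figures rest on assumed values for users at entry, start rate, dropout and the link to outcome. They are not estimates for this trial. The main efficacy analyses are not affected.

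**What to change.** In SAP 5.1, define the default split as corticosteroid use at the first Study 019 dose, matching the MMRM and Kaplan-Meier analyses, and repeat that definition where sections now say only yes/no. Show boys who start steroids on study as a separate row or column.

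For adverse event rates, including hypertension, also present events and person-time by current steroid use, split at steroid start and stop dates. This is a necessary part of the change, because the first-dose split alone would count events after an on-study start as non-user events.

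Cost: a cheap improvement. The baseline variable already exists for the models. The downside is one time-varying derivation from concomitant-medication dates that are already collected. Steroid records with imputed dates should be flagged: under SAP 6.4.2.1 a start date lacking day and month, in the year of first dose, is set to the first-dose date and could turn a later starter into a user at first dose. Protocol 10.3 gives no timing for steroid use, so the change does not conflict with it.

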5.2 Subject Disposition

A summary of subjects who discontinued ataluren treatment prematurely or were removed from the study prematurely will be reported for overall subjects, a subgroup of subjects with corticosteroid use (Yes/No), and a subgroup of ambulatory/non-ambulatory subjects at study entry. Reasons for treatment early discontinuations will be described. The number of subjects from PTC124-007 (Study 007) to Study 019 will also be reported.

Since the sponsor has decided to discontinue the Study 019, subjects who discontinue the study due to this reason or complete the study per protocol will be considered as censored in the time to discontinuation analysis. The time to discontinuation (in weeks) is calculated as $(\text{discontinuation date} - \text{first dose date} + 1)/7$ for subjects who discontinue from the study due to reasons other than sponsor's decision of termination the study or transitioning to commercial drug. For subjects who discontinue due to these reasons or complete the study, the censor time is $(\text{discontinuation date} - \text{first dose date} + 1)/7$ and $(\text{study completion date} - \text{first dose date} + 1)/7$, respectively. Time to discontinuation will be assessed using Kaplan-Meier methods and the Kaplan-Meier curve will be displayed.

The protocol deviations will be summarized by type. A listing of protocol deviations will be provided.

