6.2. Study Drug Treatment

6.2.1. Duration of Therapy

Treatment with ataluren in the context of this protocol is anticipated to occur for 240 weeks. The actual duration of ataluren treatment under this protocol will be subject to the following conditions:

- The patient has the right to withdraw consent and discontinue ataluren at any time.
- If the patient's condition substantially worsens after initiating ataluren treatment, the patient
 will be carefully evaluated by the investigator in consultation with the PTC Therapeutics
 medical monitor. The patient will be withdrawn from treatment if continuing would place
 them at risk.
- Upon consultation with the PTC Therapeutics medical monitor, the investigator may withdraw the patient from ataluren treatment, if, in the investigator's clinical judgment, it is not in the patient's best interest to continue.
- The patient will be withdrawn from treatment if he is unable to tolerate ataluren.
- The patient may be withdrawn from this study if he is eligible to participate in another ataluren - nmDBMD clinical study or program.
- This study may be discontinued by the relevant regulatory authority and/or PTC Therapeutics at any time.
- This study may be stopped upon ataluren marketing authorization within the relevant country.

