1 OVERVIEW

This statistical analysis plan (SAP) details the statistical methods to be used in the analyses and presentation of the data collected in Study PTC124-GD-019-DMD, also referred to as Study 019. Preparation of this SAP incorporates statistical design elements present in the protocol Version 5.0 (dated 18 November 2015). Details are documented in Sections 1-7.

In addition to the protocol defined analyses, a natural history control using the Cooperative International Neuromuscular Research Group (CINRG) will be utilized in order to help to better understand the long-term ataluren data. The planned analysis will be presented in Section 8.

After the implement of protocol Version 5.0, the sponsor has developed the protocol Version 6.1 (dated 08 March 2017) specifically for Canadian sites only for ethics approval when they finished all visits per Version 5.0 and were waiting to roll into another open-label nmDMD Study PTC124-GD-016-DMD conducted in the United States (US). The maximal scheduled visit in Version 5.0 was extended from week 240 to week 336 in Version 6.1. All data collected based on both Versions will be summarized together.

Where conflicts exist between this SAP and the study protocols, the information contained in this SAP supersedes the protocol.

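### SAP 5.2 counts transfer to another ataluren study as a discontinuation event, while a switch to commercial ataluren is censored, and leaves Version 6.1 roll-overs unclassified

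*SAP*

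**What the plan says.** SAP 5.2 (Subject Disposition) notes that the sponsor has decided to end Study 019, and says that "subjects who discontinue the study due to this reason or complete the study per protocol will be considered as censored". It then defines the event time "for subjects who discontinue from the study due to reasons other than sponsor's decision of termination the study or transitioning to commercial drug". Read together, these give three censored exits: sponsor termination, transition to commercial ataluren, and completion per protocol. Anything else is an event. The output is stated as follows: "Time to discontinuation will be assessed using Kaplan-Meier methods and the Kaplan-Meier curve will be displayed".

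The protocol has one more exit that bears on this. Section 6.2.1 lists among the conditions on treatment duration: "The patient may be withdrawn from this study if he is eligible to participate in another" ataluren nmDBMD study or program. Section 9 repeats it.

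SAP 1 (Overview) describes a group for whom this exit was expected. Protocol Version 6.1 was written "specifically for Canadian sites only for ethics approval when they finished all visits per Version 5.0", and those subjects "were waiting to roll into another open-label nmDMD Study PTC124-GD-016-DMD". It adds: "The maximal scheduled visit in Version 5.0 was extended from week 240 to week 336 in Version 6.1". Data from both versions are pooled.

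**The concern.** A boy who switches to commercial ataluren and a boy who moves to ataluren in another study are in the same position: both leave Study 019 and both stay on drug. The SAP censors the first and, on its literal text, counts the second as an event. It gives no reason for the difference. If the curve is read as persistence on ataluren, each transfer before completion biases it downward.

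A second gap concerns boys followed under Version 6.1. They had finished the Version 5.0 visits, but Version 6.1 runs to Week 336. The SAP does not say which version defines completion, so a boy who leaves for Study 016 at, say, Week 280 could be classed either way. Everyone else is due to finish at Week 240, so the risk set beyond that point consists only of these boys, and each exit coded as an event makes a large step.

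What is at stake is how a displayed retention curve is read in a study whose objective includes long-term tolerability.

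**Working it through.** The documents give no retention figure to reproduce. The calculation shows how far the classification can move the curve.

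**Inputs from the documents.** The planned number is up to about 96 (SAP 3.4). The last Version 5.0 visit is Week 240 (Protocol 7.2.1.3). Follow-up under Version 6.1 runs to Week 336, at Canadian sites only (SAP 1).

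**Assumed inputs, not in the documents.** N = 96. Ten genuine discontinuations are spaced evenly from Week 10 to Week 208, six of them before Week 120.5 and four after. In part A, m = 2, 5 or 10 boys transfer at Week 120.5. In part B, k Version 6.1 boys leave for Study 016 between Weeks 245 and 336. All Version 5.0 completers are censored at Week 240.

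**Formula.** Kaplan-Meier: S(t) = product over event times of (1 − d/n), where d is the number of events and n the number at risk.

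**A. Transfers before Week 240**

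- As events: nobody is censored before Week 240, so S(240) = (96 − 10 − m)/96.
- As censored: S(240) = (90/96) × (86 − m)/(90 − m). The first factor is the six early events; the second is the four later events among the 90 − m boys still at risk.

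| Transfers m | As events | As censored | Difference |
|---|---|---|---|
| 2 | 84/96 = 0.875 | (90/96)(84/88) = 0.895 | 0.020 |
| 5 | 81/96 = 0.844 | (90/96)(81/85) = 0.893 | 0.050 |
| 10 | 76/96 = 0.792 | (90/96)(76/80) = 0.891 | 0.099 |

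Censoring the transfers leaves the estimate close to the 86/96 = 0.896 that would be seen with no transfers at all.

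**B. Exits to Study 016 after Week 240 (no earlier transfers)**

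S(240) = 86/96 = 0.896, and only the k Version 6.1 boys remain at risk.

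- All exits censored: S stays at 0.896 for any k.
- All exits counted as events: the first step multiplies S by (k − 1)/k, giving 0.597 for k = 3 and 0.717 for k = 5. The last exit takes S to 0 for any k.
- All events except the last boy, who is censored: S ends at 0.896/k, which is 0.299 (k = 3), 0.179 (k = 5) or 0.090 (k = 10).

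**The case against.** The strongest objection concerns the tail. A reader might infer that the curve must fall to zero after Week 240 because every Canadian boy rolls into Study 016. The documents do not support that. SAP 1 says these boys had finished all Version 5.0 visits, so classing them as completers, and hence censored, is a natural reading. Some exits could instead be recorded as due to the sponsor's decision, which is also censored. Version 6.1 is not among the documents, so its definition of completion cannot be checked. Any Kaplan-Meier curve reaches zero if everyone left at risk is assigned an event; the zero in part B is that assumption carried through, and a median read off such a tail would depend on assumed exit dates. This part of the objection stands. What remains for Version 6.1 is an unspecified classification.

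A second objection is that little depends on the curve. Time to discontinuation sits under Subject Disposition and is not a listed endpoint. SAP 5.2 promises a curve and names no median. Reasons for early treatment discontinuation are described in SAP 5.2, and adverse events leading to discontinuation are tabulated and listed under SAP 5.7.1. This also stands, and it limits the importance of the point. A reader should not infer that the curve is the study's main measure of tolerability.

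Neither objection answers the transfer before Week 240. That boy has completed neither version and has not gone to commercial drug. Unless his exit is recorded as due to study termination, the written rule makes him an event.

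**Conclusion.** The concern holds in two parts of different strength.

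For transfers before completion, the rule as written treats continuation of ataluren in another study as a discontinuation and is inconsistent with its own handling of commercial transitions. Under the assumed inputs, Week-240 retention is understated by about 2, 5 or 10 percentage points for 2, 5 or 10 transfers. The documents do not say how many boys transferred, so the actual effect may be nil or small.

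For Version 6.1 boys who leave for Study 016 after Week 240, the SAP does not settle the classification. With 10 earlier discontinuations, the end of the curve can lie anywhere from 0.896 to zero. A fall to zero needs both that these exits are coded as neither completion nor sponsor decision, and that the last boy followed leaves by roll-over. Neither condition is established.

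The analysis is descriptive. No hypothesis test, sample size or primary endpoint is affected.

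**What to change.** In SAP 5.2:

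- Add that any subject who leaves Study 019 to continue ataluren in another ataluren study or program, including Study 016, is censored at the exit date, as is already done for transition to commercial drug.
- State that Version 6.1 subjects who finished the Version 5.0 visits and then roll over are censored and are not events.
- Print the numbers at risk under the curve, so that the small risk set after Week 240 is visible.
- List the transfers by destination.

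The cost is one or two sentences, one rerun figure and a short listing. Protocol section 9 already requires the date and reason for discontinuation to be recorded in the eCRF. The downside is that a transfer concealing a tolerability problem would be censored; the listing allows each such case to be examined.
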